2.1 Inclusion and exclusion criteria

Criterion 1. Adult patient

- “1. Adult patient” in the ELIGIBILITY CRITERIA form [**EC. EC_IC_1**] = “Yes” AND
- “1. Adult patient” in the PROTOCOL DEVIATION FORM [**PDF. PDF_IC1**] is not flagged AND
- “Age at start of first-line treatment” [**PI. PI_age**] is not missing AND
- the age recorded in the field “Age at start of first-line treatment” [**PI. PI_age**] is coherent with the definition of adult patient which applies to the specific country (minimum age to be provided by the [REDACTED] according to the Data Validation Plan specifications).

Criterion 2. Diagnosed with Epidermal Growth Factor Receptor Tyrosine Kinase Inhibitor (EGFR-TKI) naïve advanced EGFR mutated non-small cell lung cancer (NSCLC)

- “2. Diagnosed with Epidermal Growth Factor Receptor Tyrosine Kinase Inhibitor (EGFR-TKI) naïve advanced EGFR mutated non-small cell lung cancer (NSCLC)” in the ELIGIBILITY CRITERIA form [**EC. EC_IC_2**] = “Yes” AND
- “2. Diagnosed with Epidermal Growth Factor Receptor Tyrosine Kinase Inhibitor (EGFR-TKI) naïve advanced EGFR mutated non-small cell lung cancer (NSCLC)” in the PROTOCOL DEVIATION FORM [**PDF. PDF_IC2**] is not flagged AND
- “Date of NSCLC diagnosis (dd/mmm/yyyy)” [**DIAG. DIAG_date**] is not missing (at least year shall be known)(*) AND
- “Date of NSCLC diagnosis (dd/mmm/yyyy)” [**DIAG. DIAG_date**] ≤ Start date of the Index EGFR-TKI therapy (as defined in Chapter 3) AND
- NSCLC stage at start of first-line treatment (as defined in Chapter 3) not missing

(*) if the year is not provided, a query will be raised. If the year cannot be retrieved, the Sponsor will evaluate the opportunity to consider the patient as violator or not for this criterion.

Criterion 3. Treated for Epidermal Growth Factor Receptor (EGFR) mutated NSCLC within regular clinical practice.

- “3. Treated for Epidermal Growth Factor Receptor (EGFR) mutated NSCLC within regular clinical practice)” in the ELIGIBILITY CRITERIA form [**EC. EC_IC_3**] = “Yes” AND
- “3. Treated for Epidermal Growth Factor Receptor (EGFR) mutated NSCLC within regular clinical practice)” in the PROTOCOL DEVIATION FORM [**PDF. PDF_IC3**] is not flagged AND
- “Number of treatment lines for advanced EGFR-mutated NSCLC within date of data collection” [**PI. PI_num_lines**] is not missing (since all patients shall have received at least one line).

Criterion 4. Informed and privacy consent signature obtained depending on local regulations

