- “4. Informed and privacy consent signature obtained depending on local regulations” in the ELIGIBILITY CRITERIA form [**EC. EC_IC_4**] = “Yes” OR “Not applicable: ICF waiver/Opt-out/No opposition applies”, AND
- “4. Informed and privacy consent signature obtained depending on local regulations” in the PROTOCOL DEVIATION FORM [**PDF. PDF_IC4**] is not flagged AND
- “Date of data collection (dd/mmm/yyyy)” [**PI. PI_date_coll**] is not missing.

Moreover, for patients with “4. Informed and privacy consent signature obtained depending on local regulations” in the ELIGIBILITY CRITERIA form [**EC. EC_IC_4**] = “Yes, it will be also verified that:

- “Date of informed consent form signature by the patient or by next of kin* (dd/mmm/yyyy)” [**PI. PI_date_IC**] <= “Date of data collection (dd/mmm/yyyy)” [**PI. PI_date_coll**] AND
- “Date of privacy form signature by the patient or by next of kin* (dd/mmm/yyyy)” [**PI. PI_date_priv**] <= “Date of data collection (dd/mmm/yyyy)” [**PI. PI_date_coll**]

During data elaboration this criterion will be critically reviewed and discussed, depending also on specificities of sites and countries local regulations.

Criterion 5 (UNCOMMON MUTATION COHORT). Patient harbouring uncommon or compound EGFR mutations

- “Cohort” [**PI. PI_coh_ty**] = “Uncommon Mutation cohort” AND
- “5. Patient harbouring uncommon or compound EGFR mutations” in the ELIGIBILITY CRITERIA form [**EC. EC_IC_5umc**] = “Yes” AND
- “5. Patient harbouring uncommon or compound EGFR mutations” in the PROTOCOL DEVIATION FORM [**PDF. PDF_IC5_umc**] is not flagged AND
- At least one uncommon mutation shall be present on the start date of the Index EGFR-TKI therapy (as defined in “Chapter 3”), according to the fields:
 - “EGFR mutations at start of first-line treatment” [**First-line treatment period / MUT1. MUT1_unc**]
OR
 - “EGFR mutations at start of second-line treatment” in the MUTATIONS form of the [**Second-line treatment period / MUT2. MUT2_mut_start**]

Criterion 5 (SEQUENCING COHORT). Patient with common EGFR mutations (Del19, L858R)

- “Cohort” [**PI. PI_coh_ty**] = “Sequencing cohort” AND
- “5. Patient with common EGFR mutations (Del19, L858R)” in the ELIGIBILITY CRITERIA form [**EC. EC_IC_5sc**] = “Yes” AND
- “5. Patient with common EGFR mutations (Del19, L858R)” in the PROTOCOL DEVIATION FORM [**PDF. PDF_IC5_sc**] is not flagged AND

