- “EGFR mutations at start of first-line treatment” [**First-line treatment period / MUT1. MUT1_seq**] = “Del19” OR “L858R”

Criterion 6 (UNCOMMON MUTATION COHORT). Patient who started with either afatinib (Giotrif), gefitinib (Iressa), erlotinib (Tarceva), or osimertinib (Tagrisso) in the first- or second-line setting within regular clinical practice

- “Cohort” [PI. PI_coh_ty] = “Uncommon Mutation cohort” AND
- “6. Patient who started with either afatinib (Giotrif®), gefitinib (Iressa), erlotinib (Tarceva), or osimertinib (Tagrisso) in the first- or second-line setting within regular clinical practice” in the ELIGIBILITY CRITERIA form [EC. EC_IC_6umc] = “Yes” AND
- “6. Patient who started with either afatinib (Giotrif®), gefitinib (Iressa), erlotinib (Tarceva), or osimertinib (Tagrisso) in the first- or second-line setting within regular clinical practice” in the PROTOCOL DEVIATION FORM [PDF. PDF_IC6_umc] is not flagged AND
- “Type of treatment” [First-line treatment period / TREAT. TREAT_ty] = “EGFR-TKI” OR “Type of treatment” [Second-line treatment period / TREAT. TREAT_ty] = “EGFR-TKI” AND
- The EGFR-TKI ADMINISTRATION DETAILS form [name of the form: EAD] is not empty

Criterion 6 (SEQUENCING COHORT). Patient was treated with afatinib (Giotrif®) in the first-line setting and for acquired T790M mutation with osimertinib in the second line

- “Cohort” [PI. PI_coh_ty] = “Sequencing cohort” AND
- “6. Patient was treated with afatinib (Giotrif®) in the first-line setting and for acquired T790M mutation with osimertinib in the second line” in the ELIGIBILITY CRITERIA form [EC. EC_IC_6sc] = “Yes” AND
- “6. Patient was treated with afatinib (Giotrif®) in the first-line setting and for acquired T790M mutation with osimertinib in the second line” in the PROTOCOL DEVIATION FORM [PDF. PDF_IC6_sc] is not flagged AND
- “Number of treatment lines for advanced EGFR-mutated NSCLC within date of data collection” [PI. PI_num_lines] = “2” OR “>2” AND
- The AFATINIB ADMINISTRATION DETAILS form [name of the form: AAD] is not empty AND earliest “Start date with this dose (dd/mmm/yyyy)” [AAD. AAD_start_date] is not missing, AND
- The OSIMERTINIB ADMINISTRATION DETAILS form [name of the form: OAD] is not empty AND earliest “Start date with this dose (dd/mmm/yyyy)” [OAD. OAD_start_date] is not missing, AND
- The earliest start date in the OSIMERTINIB ADMINISTRATION DETAILS form is greater than the earliest start date in the AFATINIB ADMINISTRATION DETAILS form, AND

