- “EGFR mutations at start of second-line treatment” [Second-line treatment period / MUT2. MUT2_mut_start] includes “T790M”

Criterion 7 (UNCOMMON MUTATION COHORT). Patient has started EGFR-TKI treatment at least 12 months prior to data entry

- “Cohort” [PI. PI_coh_ty] = “Uncommon Mutation cohort” AND
- “7. Patient has started EGFR-TKI treatment at least 12 months prior to data entry” in the ELIGIBILITY CRITERIA form [EC. EC_IC_7umc] = “Yes” AND
- “7. Patient has started EGFR-TKI treatment at least 12 months prior to data entry” in the PROTOCOL DEVIATION FORM [PDF. PDF_IC7_umc] is not flagged AND
- Start date of the Index EGFR-TKI therapy (as defined in “Chapter 3”) is lower than or equal to (“Date of data collection (dd/mmm/yyyy)” [PI. PI_date_coll] – 11.50 months) (*)

This line shall start in presence of at least one uncommon/compound mutation (as described in the definition of the calculated variable “Index EGFR-TKI therapy”: see “Chapter 3”).

(*) this means that if the start date of the index EGFR-TKI therapy is 11.49 months before date of data collection, the patient violates this criterion. This tolerance window has been agreed with the Sponsor during the Data Analysis Strategic Meeting, and will not be further discussed. Only in case exact day is not known and this makes the evaluation critical with the respect to the tolerance window, then case-by-case discussion will be done with the Sponsor.

In case the Index therapy line is an EGFR-TKI given in combination with chemotherapy, a query will be raised in order to ensure that the treatment line was administered according to regular clinical practice.

Criterion 7 (SEQUENCING COHORT). Patient has started osimertinib treatment at least 10 months prior to data entry

- “Cohort” [PI. PI_coh_ty] = “Sequencing cohort” AND
- “7. Patient has started osimertinib treatment at least 10 months prior to data entry” in the ELIGIBILITY CRITERIA form [EC. EC_IC_7sc] = “Yes” AND
- “7. Patient has started osimertinib treatment at least 10 months prior to data entry” in the PROTOCOL DEVIATION FORM [PDF. PDF_IC7_sc] is not flagged AND
- Start date of the Index EGFR-TKI therapy (as defined in “Chapter 3”) is lower than or equal to (“Date of data collection (dd/mmm/yyyy)” [PI. PI_date_coll] – 9.50 months) (*)

This line shall start in presence of at least one common mutation (as described in the definition of the calculated variable “Index EGFR-TKI therapy”: see “Chapter 3”).

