2.5 Hierarchy of violated criteria

The purpose of this algorithm is to assign an unique, major criteria violation to each enrolled patients, even in case a patient has more than one reason (ie. more than one criterion) for being excluded from the analysis.

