- from the OSIMERTINIB ADMINISTRATION DETAILS form (only for the SEQUENCING COHORT), from the field [OAD. OAD_dose] of the record with earliest non-missing start date (recorded in field [OAD. OAD_start_date]);
- from the EGFR-TKI ADMINISTRATION DETAILS form (only for the UNCOMMON MUTATION COHORT), from the field [EAD. EAD_dose] of the record with earliest non-missing start date (recorded field [EAD. EAD_start_date]). The same patient could have one or two lines of EGFR-TKI recorded in this form, and each line is identified by the field "Type of EGFR-TKI" [EAD. EAD_EGFR]: therefore, for each line recorded in this form, it will be possible to identify the starting dose with the rule defined above.

Index EGFR-TKI therapy

- *Uncommon mutation cohort*: it will correspond to the therapy recorded in the NSCLC TREATMENT form, either at [First-line treatment period] or [Second-line treatment period] depending on the following conditions:
 - [First-line treatment period] is the time point to consider if:
 - “Type of treatment” [First-line treatment period / TREAT. TREAT_ty] = “EGFR-TKI” AND
 - “Start date of this line (dd/mmm/yyyy)” [First-line treatment period / TREAT. TREAT_start_date] is lower than or equal to (“Date of data collection (dd/mmm/yyyy)” [PI. PI_date_coll] – 11.50 months) AND
 - “EGFR mutations at start of first-line treatment” [First-line treatment period / MUT1. MUT1_unc] has at least one of the options selected (excluding “Del19” and “L858R”) (*)
 - Otherwise, if the above-specified condition is not met, then the [Second-line treatment period] is the time point to consider if:
 - “Type of treatment” [Second-line treatment period / TREAT. TREAT_ty] = “EGFR-TKI” AND
 - “Start date of this line (dd/mmm/yyyy)” [Second-line treatment period / TREAT. TREAT_start_date] is lower than or equal to (“Date of data collection (dd/mmm/yyyy)” [PI. PI_date_coll] – 11.50 months) AND
 - “EGFR mutations at start of first-line treatment” [First-line treatment period / MUT1. MUT1_unc] OR “EGFR mutations at start of second-line treatment” in the MUTATIONS form of the [Second-line treatment period / MUT2. MUT2_mut_start] has at least one of the options selected (excluding “Del19” and “L858R”) (*)

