4.1 UNCOMMON MUTATION COHORT

4.1.1 Patient disposition, analysis sets and criteria violations

Table 1-UNC. Patient disposition (ENROLLED PATIENTS of the Uncommon Mutation Cohort)

For each center, the table will provide absolute and relative frequencies of:

- patients ENROLLED in the UPSWING study (as defined in Chapter 2.3) in the cohort
- patients ELIGIBLE for the UPSWING study (as defined in Chapter 2.3) in the cohort

Percentages will be calculated by column; percentages will be calculated by row only for "Overall in the cohort".

Figure 1-UNC. Workflow of analysis sets and reasons for violations (ENROLLED PATIENTS of the Uncommon Mutation Cohort)

A figure with the workflow of analysis sets and reasons for violations will be provided; the hierarchy of violated criteria specific for the cohort (as defined in Section 2.5) will be applied, so that each violator will be classified with only one major violation (even in case of multiple violations).

Table 2-UNC. Reasons for violations (ENROLLED PATIENTS of the Uncommon Mutation Cohort)

The table will describe the reasons for patient non-eligibility and non-evaluability (considering each criterion listed in Section 2.3).

Absolute and relative frequency distribution will be provided.

For each evaluability criterion, percentages will be computed out of the total number of enrolled patients in the cohort.

Table 3-UNC. Duration of observation (ELIGIBLE PATIENTS of the Uncommon Mutation Cohort)

The table will provide main descriptive statistics (mean, standard deviation, quartiles, min, max) of duration of observation window (in months) starting from the first-line treatment start (see "Computed variables" chapter)

Descriptives will be calculated over the number of ELIGIBLE PATIENTS in the cohort.

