- R-DMS will perform an overall conceptual review of results, in order to evaluate their coherence and plausibility. Moreover, all the tables in this report will be independently reviewed to verify their consistency.
- Moreover, the following tables will be reprogrammed or independently verified (by another [REDACTED], as detailed for each point):

For UNCOMMON MUTATION COHORT report:

- Table 1-UNC. Patient disposition (ENROLLED PATIENTS of the Uncommon Mutation Cohort): [REDACTED]/another BS will independently recalculate frequencies
- Table 2-UNC. Reasons for violations (ENROLLED PATIENTS of the Uncommon Mutation Cohort): [REDACTED]/another BS will independently recalculate frequencies and check the algorithms for each criterion for 100% of enrolled patients
- Table 8-UNC. Sites of metastases (ELIGIBLE PATIENTS of the Uncommon Mutation Cohort): [REDACTED]/another BS will independently recalculate descriptive statistics and check the algorithm for 10% of analyzed patients
- Table 10-UNC. Approaches for detection of mutations at first-line treatment start (ELIGIBLE PATIENTS of the Uncommon Mutation Cohort) – Secondary objective #3: formatted table will be checked against the raw output
- Table 12-UNC. Mutations at second-line treatment start (ELIGIBLE PATIENTS of the Uncommon Mutation Cohort): [REDACTED]/another BS will independently recalculate descriptive statistics and check the algorithm for 10% of analyzed patients
- Table 18-UNC. NSCLC treatment patterns (ELIGIBLE PATIENTS of the Uncommon Mutation Cohort): [REDACTED]/another BS will independently recalculate descriptive statistics and check the algorithm for 10% of analyzed patients
- Table 31-UNC. Details of index EGFR-TKI treatment (ELIGIBLE PATIENTS of the Uncommon Mutation Cohort): [REDACTED]/another BS will independently recalculate descriptive statistics and check the algorithm for 10% of analyzed patients
- Table 34-UNC. Index EGFR-TKI therapy patterns (ELIGIBLE PATIENTS of the Uncommon Mutation Cohort): [REDACTED]/another BS will independently recalculate descriptive statistics and check the algorithm for 10% of analyzed patients

- Table 35-UNC. Response to index EGFR-TKI treatment (ELIGIBLE PATIENTS of the Uncommon Mutation Cohort) – Secondary objective #1: formatted table will be checked against the raw output

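### Criteria 2 and 7 are tested on an Index EGFR-TKI date that exists only if the follow-up and mutation conditions are already met, so Figure 1 reports wrong exclusion reasons

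*SAP*

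**What the plan says.** All references are to the SAP.

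- **Criterion 2 (section 2.1, both cohorts).** The diagnosis date must be on or before the index start: "Start date of the Index EGFR-TKI therapy (as defined in Chapter 3) AND".
- **Index definition, uncommon cohort (Chapter 3).** The first line is the index if it is an EGFR-TKI, started at least 11.50 months before data collection, and an EGFR mutation other than Del19 or L858R is recorded. The only fallback is the second line, on matching conditions: "Otherwise, if the above-specified condition is not met, then the [Second-line treatment period] is the time point to consider if".
- **Index definition, sequencing cohort (Chapter 3).** Osimertinib is the index if it started at least 9.50 months before data collection and T790M is recorded at second-line start.
- **Criterion 7 (section 2.1).** The index start is tested against the same cut-offs. The uncommon-cohort footnote says "if the start date of the index EGFR-TKI therapy is 11.49 months before date of data collection, the patient violates this criterion". The sequencing footnote says the same for 9.49 months.
- **Criterion 5 (section 2.1).** Uncommon cohort: "At least one uncommon mutation shall be present on the start date of the Index EGFR-TKI therapy". The sequencing version reads a mutation field and makes no use of the index: "MUT1_seq] = “Del19” OR “L858R".
- **Hierarchy (section 2.5).** Its purpose is to "assign an unique, major criteria violation to each enrolled patients, even in case a patient has more than one reason". The order is Criterion 4 (rank 1), 1 (2), 2 (3–4), 3 (5–6), 5 (7–8), 6 (9–10), 7 (11–12). Section 2.5.2 applies it to the sequencing cohort too.
- **Figure 1 (section 4.1.1).** "the hierarchy of violated criteria specific for the cohort (as defined in Section 2.5) will be applied", giving one reason per violator. The Table 2 layout in section 5.1.1 is not hierarchical and notes that a patient may violate several criteria.

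**The concern.** The follow-up and mutation conditions are used twice: once to decide whether an index exists, and again as criteria that refer to that index. A patient who fails one of them has no date for Criterion 2 to be compared with, and no rule covers that case. Because Criterion 2 stands high in the hierarchy, it takes the label from the criterion that was actually failed.

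Figure 1 is where readers of this retrospective study learn who was left out and why. The protocol treats selection as a main limitation (sections 9.9 and 9.12) and sets its 12- and 10-month thresholds to avoid early censoring (section 9.2.1). Reporting those exclusions as failures of the diagnosis criterion misdescribes how the cohorts were formed.

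**Working it through.** No sample-size or event figure is involved. The check applies the written rules to constructed patients.

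**Step 1: what an undefined index means.** Section 2.3 admits to ELIGIBLE only patients who meet every criterion, so a comparison with a date that does not exist is not met. If the check were skipped instead, a patient at 11.49 months would pass every computed criterion check, against the footnote's stated result. Skipping is therefore not a workable reading.

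**Step 2: uncommon-cohort profiles.** Times are months before data collection. Column A treats an undefined index as not met. Column B assumes the code lets a missing date sort below every real date and reads Criterion 5 from the mutation fields alone.

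| Profile | Index | Failed, A | Failed, B | Figure 1 |
|---|---|---|---|---|
| TKI at 20, uncommon mutation, diagnosed at 30 | 20 | none | none | eligible |
| TKI at 11.50, uncommon mutation, diagnosed at 13 | 11.50 | none | none | eligible |
| TKI at 11.49, uncommon mutation, diagnosed at 13 | none | 2, 5, 7 | 2 | Criterion 2 |
| TKI at 20, no uncommon mutation | none | 2, 5, 7 | 2, 5 | Criterion 2 |
| No TKI line, uncommon mutation | none | 2, 5, 6, 7 | 2, 6 | Criterion 2 |
| Chemotherapy at 20, second-line TKI at 6, uncommon mutation | none | 2, 5, 7 | 2 | Criterion 2 |

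The Figure 1 label is the same in A and B. What Table 2 shows for Criteria 5 and 7 is not.

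**Step 3: sequencing-cohort profiles (reading A).** Osimertinib at 9.49 months fails 2 and 7 and is labelled 2. No T790M fails 2, 6 and 7 and is labelled 2. No common mutation, with T790M and osimertinib at 15 months, has an index, fails 5 only and is correctly labelled 5.

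**Step 4: a grid of uncommon-cohort profiles.** First line TKI or chemotherapy (2); first-line start at 6, 11.49, 11.5, 14 or 24 months (5); uncommon mutation at first line yes or no (2). With no second line: 2 × 5 × 2 = 20. With a second line of TKI or chemotherapy (2), started 2, 8 or 12 months later (3), mutation at second line yes or no (2): 20 × 2 × 3 × 2 = 240. Total 260. Diagnosis was set at 40 months throughout, so no profile has a late diagnosis date.

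- As written (reading A): 55 eligible, 205 ineligible, all 205 labelled Criterion 2.
- Tested on recorded TKI lines: the same 55 eligible; the 205 become 85 under Criterion 5, 70 under Criterion 7 and 50 under Criterion 6 (85 + 70 + 50 = 205).
- Profiles with a defined index that failed the Criterion 7 date check: 0.

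**Step 5: why the eligible set does not move.** An uncommon-cohort patient without an index has no TKI line (fails 6), a TKI line but none with a qualifying mutation (fails 5), or a qualifying line that is too recent or undated (fails 7). A sequencing patient without an index lacks T790M or an osimertinib start date (fails 6) or started too recently (fails 7). Each is ineligible anyway.

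**The case against.** The best reply is that nothing of consequence changes: no estimate moves, Table 2 lists every violated criterion, and the footnotes make plain that 11.49 and 9.49 months are meant to fall under Criterion 7. A competent programmer would see this. Much of that stands. Table 2 still shows no-TKI and no-T790M patients under Criterion 6. It also gains a spurious Criterion 2 failure, however, and the footnotes' intention conflicts with Chapter 3, where such a line cannot be the index.

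A reader might infer more than the documents support:

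- **That every failure of Criteria 5, 6 or 7 is mislabelled.** A violation marked only on the eligibility or deviation form is labelled correctly if the data still give an index. So is an empty EGFR-TKI administration form, because the index start comes from the treatment form.
- **That Criterion 5 is circular in both cohorts.** The sequencing version does not use the index. In the uncommon cohort the criterion also names the mutation fields, so a too-recent starter need not be counted as lacking a mutation.
- **That SAS would pass Criterion 7 for the patients it should catch.** That depends on code not yet written. If undefined is coded as not met, Criterion 7 fails in Table 2.
- **That quality control would repeat the error.** The second check is to "independently recalculate frequencies and check the algorithms for each criterion for 100% of enrolled patients". Working from this text it might reproduce the labels, but section 6 also requires a plausibility review of the results.

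**Conclusion.** The rule is wrong as written. Patients not already labelled under Criterion 4 or 1, and whose recorded data give no index, appear in Figure 1 under Criterion 2 instead of under their true reason, in both cohorts. The Criterion 7 date check has no power to exclude on a defined index, which contradicts its own footnotes.

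The damage is confined to reported exclusion reasons. It would be tempting to conclude that the analysed population or the Kaplan-Meier results are biased; Step 5 shows that they are not. How many real patients are affected cannot be stated, because the documents give no count of enrolled violators, and the 205 of 260 describes test profiles only. The conclusion assumes that an undefined index means the comparison is not met. The SAP does not say so, but it follows from section 2.3, and the missing-sorts-lowest convention gives the same Figure 1 label. The point is worth correcting before the tables are produced.

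**What to change.** - **(a) Criterion 2.** Compare the diagnosis date with the start of first-line therapy, already computed in Chapter 3, using only the date parts recorded. Section 2.1 accepts a year-only diagnosis and Chapter 3 imputes it to 1 July, which could exclude an eligible patient treated earlier that year; compare such dates by year. Apparent conflicts raise a query and do not exclude automatically. State that an undefined index is never by itself a Criterion 2 violation.
- **(b) Criterion 5, uncommon cohort.** If there is an EGFR-TKI line, require an option other than Del19 or L858R in `MUT1_unc` (first-line TKI), or in `MUT1_unc` or `MUT2_mut_start` (second-line TKI). If there is no TKI line, read the mutation fields alone, so that the failure falls under Criterion 6. Defining Criterion 5 simply as the existence of a TKI line with a mutation would not do: it would send no-TKI patients to Criterion 5, which ranks above 6.
- **(c) Criterion 7, uncommon cohort.** Test 11.50 months on the recorded, non-missing start of the earliest TKI line with a qualifying mutation, or of the earliest TKI line if none qualifies. Do not assess it when there is no TKI line.
- **(d) Sequencing cohort.** Test T790M only in Criterion 6, and 9.50 months in Criterion 7 on the earliest non-missing `OAD_start_date`. Also reconcile the Criterion 7 text, which attributes a common-mutation condition to the index definition, with Chapter 3, which requires T790M.
- **(e) Index variable.** Leave it unchanged for the endpoints, and keep a defined index as a condition of ELIGIBLE.

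The cost is SAP wording, minor recoding and a few extra date queries, with no new data items. Only part (a) can touch eligibility, and only for patients whose diagnosis date appears to conflict with treatment start, who go to query.
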